Study Design	
This is a randomized, double-blind, placebo-controlled, Phase 1 clinical trial in which a total of 60 subjects will receive one of three doses of Invaplex_{AR}-DETOX or placebo (saline), as shown in the table below. The vaccine will be administered via IM injection on study days 1, 22, and 43. Each subject will receive the same formulation at each vaccination dependent upon group assignment.
 
The study will be initiated with the lowest dose level (2.5 µg) and will proceed to the next highest dose in an escalating fashion. A dose-level with no occurrence of stopping criteria in the 7 days following the third vaccine dose will prompt moving to the next higher level. All safety data will be summarized and reviewed by the PSRT prior to dose-escalation.
 
For the initial cohort, enrollment will be limited initially to 4 subjects receiving 2.5 µg of Invaplex_{AR}-DETOX alone and 1 subject receiving placebo. If no unexpected symptoms occur within 7 days following initial vaccination, enrollment of the remaining subjects in the cohort may proceed.
 
  
 Cohort	Group	n	Route	Invaplex_{AR}-DETOX (µg)	
   
 A	A-1	16	IM	2.5	
 
 A-2	4	IM	Placebo	
 
 B	B-1	16	IM	10	
 
 B-2	4	IM	Placebo	
 
 C	C-1	16	IM	25	
 
 C-2	4	IM	Placebo	
  
 
Specimens will be collected at prescribed intervals to examine systemic and mucosal immune responses. Vaccine safety will be actively monitored during vaccination and for 28 days following the third vaccine dose. Additionally, a telephone follow-up will be performed at 6 months following receipt of the final vaccination to assess for adverse events.
	Cohort	Group	n	Route	Invaplex _{AR} -DETOX (µg)	A	A-1	16	IM	2.5	A-2	4	IM	Placebo	B	B-1	16	IM	10	B-2	4	IM	Placebo	C	C-1	16	IM	25	C-2	4	IM	Placebo
Cohort	Group	n	Route	Invaplex _{AR} -DETOX (µg)																													
A	A-1	16	IM	2.5																													
	A-2	4	IM	Placebo																													
B	B-1	16	IM	10																													
	B-2	4	IM	Placebo																													
C	C-1	16	IM	25																													

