8.5.1. Vaccination Follow-Up

The timing and number of follow-up visits are delineated in the Time and Events Schedule (Table 8) and are scheduled to coincide with vaccination or specimen collection visits. These visits may include a brief history, targeted exam, blood, stool, and salivary specimen collection, and a reminder to the volunteer to contact the investigator if s/he experiences any medical problems. Subjects will return approximately 24 hours and 7 days after vaccination for follow-up.

Approximately 6 months from final vaccination all subjects will be contacted via telephone to assess for a final safety assessment. A history for any additional serious new diagnoses or hospitalizations will be solicited. Three attempts will be made and documented; after 3 unsuccessful attempts a certified letter and/or email will be used to request the subject to contact the study team.

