11.8. Recording Adverse Events

11.8.1. Methods/Timing for Assessing, Recording, and Analyzing Safety Endpoints

AEs, solicited AEs, and SAEs will be assessed at all study visits, documented in the source records, and recorded on the eCRFs using accepted medical terms and/or the diagnoses that accurately characterize the event. When a diagnosis is known, the AE term recorded on the eCRF will be the diagnosis rather than a constellation of symptoms. The investigator will assess all AEs for seriousness, relationship to the investigational product, severity, and other possible etiologies. When an event has not resolved by the prescribed reporting period, it will be documented on the AE eCRF as "unknown."

The time frame for the collection of AEs and SAEs begins at the first administration of investigational product through 28 days after the last dose of investigational product is administered. Additionally, subjects will be contacted by telephone approximately 6 months after the final vaccination to assess for any new-onset SAEs since participation in the trial.

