8.3. Adverse Events

The primary objective of this study is safety of the Invaplex_{AR}-DETOX vaccination. All summaries of adverse events will be presented by vaccine dose (1 to 3) and overall, and by treatment group. Safety summaries and analyses will be presented for the Safety Population.

Local and general (systemic) solicited AEs, as well as lymph node assessments, are collected within 30 minutes of each vaccine dose and through 7 days following each dose (day of vaccination and subsequent 7 days). Lymph nodes are assessed as palpable or not palpable and for tenderness (yes/no). All other solicited events and symptoms are graded as 0 (normal), 1 (mild), 2 (moderate), 3 (severe), and 4 (potentially life-threatening). All general and local reactions are listed below.

Local Reactions:

- Site pain, site tenderness, swelling, induration, site redness and pruritus.

General Reactions:

- Fever, nausea, vomiting, abdominal pain, diarrhea (loose stools), appetite change, fatigue, headache, myalgias, arthralgias and malaise.

Adverse events will be summarized by MedDRA[®] system organ class (SOC), preferred term (PT), severity (mild, moderate, severe, potentially life-threatening) and whether related (definitely, probably or possibly) or not related (unrelated, unlikely) to study product. When calculating the incidence of adverse events (i.e., on a per subject basis), each subject will only be counted once per category. Per protocol, all adverse events occurring within 28 days of the third vaccination (Day 71) will be presented ([Table 18, Appendix A](#) and [Listing 10, Appendix C](#)). All events reported on the adverse event CRF will be included in the listing.

To assess safety, the number and percentage of subjects experiencing at least one AE, and the number and percentage of subjects experiencing each specific AE, categorized by body system, preferred term and product administered (for individual post-dose periods and for the entire study period) along with exact 95% CIs, will be tabulated. Overall summaries by study group include the number and percentage of subjects experiencing: (1) any adverse experience; (2) any Grade 2 or greater AE; (3) any AE judged related to study product; (4) any Grade 2 or greater AE judged related to study product; (5) Any SAE; (6) Any SAE related to IP.

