Day 29 Post-Dose 2, Day 7						x.XXXX
Day 50 Post-Dose 3, Day 7						x.XXXX
Day 71 Post-Dose 3, Day 28						x.XXXX
ALS IgG						
Baseline	n	xx				x.XXXX
	GMT	xxxx				
	95% CI	xxxx - xxxx				
Day 8 Post-Dose 1, Day 7						x.XXXX
Day 29 Post-Dose 2, Day 7						x.XXXX
Day 50 Post-Dose 3, Day 7						x.XXXX
Day 71 Post-Dose 3, Day 28						x.XXXX

GMT = Geometric Mean Titer. CI = Confidence Interval. P-values are from ANOVA tests of differences between groups in mean log titers.

Table A4: Antibody in Lymphocyte Supernatant (ALS) Responses to *S. flexneri* 2a Invaplex, Seroconversion Rates by Study Day and Treatment Group - Immunogenicity Population [In-text]

Time Point	Statistic	InvaplexAR-DETOX Dose			Placebo (N=X)	P-Value
		2.5 µg (N=X)	10 µg (N=X)	25 µg (N=X)		
ALS IgA						
Day 8	n	xx				x.XXXX
	Seroconversion %	xx.x				
	95% CI	xx.x, xx.x				
Day 29						x.XXXX
Day 50						x.XXXX
Day 71						x.XXXX
ALS IgG						
Day 8						x.XXXX
Day 29						x.XXXX
Day 50						x.XXXX
Day 71						x.XXXX

Seroconversion defined as ≥ 4 -fold increase in titer from baseline. CI = Exact Clopper Pearson Confidence Interval. P-values are from Fisher's exact 2-tail tests of differences between groups in seroconversion rates.

A.3 Safety Tables

A.3.1 Adverse Events

Table 18: Summary of Adverse Events, by Study Group - Safety Population [In-Text]

	InvaplexAR 2.5 µg (N=X)	InvaplexAR 10 µg (N=X)	InvaplexAR 25 µg (N=X)	Placebo (N=X)			
	n(%)	95%CI	n(%)	95%CI	n(%)	95%CI	P-Value*
Up to and including Visit 11 (28 days post-Dose 3).							
Any AE							
Any Grade 2 or Greater AE							
Any AE related to IP							
Any Grade 2 or greater AE related to IP							
Any SAE							
Any SAE related to IP							
After Visit 11 and up to Visit 12 (Day 223).							
Any AE							
Any Grade 2 or Greater AE							
Any AE related to IP							
Any Grade 2 or greater AE related to IP							
Any SAE							
Any SAE related to IP							

N=Number of subjects in the Safety Population. CI=Exact (Clopper-Pearson) Confidence Interval. IP=Investigational Product.

AEs include SAEs. Related = Possibly, probably or definitely related to study product.

* Pearson's Chi-square test or Fisher's exact 2-tailed test of any difference in proportions between groups. If statistically significant, significant pairwise differences will be based on non-overlapping 95% CIs.

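### SAP Table 18 reports any-AE rates, intervals and p-values for Day 71 to Day 223, when the plan seeks only serious events; those rows understate AE incidence by an amount the documents cannot size

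*SAP*

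**What the plan says.** **The table.** SAP Appendix A.3.1, Table 18, has two blocks. The first runs to Visit 11 (Day 71). The second is headed "After Visit 11 and up to Visit 12 (Day 223". Both list the same six rows: any AE, any AE of Grade 2 or more, any related AE, any related AE of Grade 2 or more, any SAE, and any related SAE. The footnotes apply to both blocks:

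- Population and interval: "N=Number of subjects in the Safety Population. CI=Exact (Clopper-Pearson) Confidence Interval".
- Test: "Pearson's Chi-square test or Fisher's exact 2-tailed test of any difference in proportions between groups".
- Content of the AE rows: "AEs include SAEs. Related = Possibly, probably or definitely related to study product".

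No footnote says that collection changes after Day 71.

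**What is collected after Day 71.** Protocol 11.8.1 closes AE collection 28 days after the last dose and describes the six-month call as one "to assess for any new-onset SAEs since participation in the trial". Protocol 8.5.1 gives the content of the call: "A history for any additional serious new diagnoses or hospitalizations will be solicited". Protocol 8.8 likewise directs the question to new serious health problems or hospital stays.

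**What the SAP text says.** SAP 3.1.1 limits the six-month part of the safety objective to serious problems and hospitalizations. SAP 3.2.1.1 ends the unsolicited AE endpoint at Day 71. SAP 8.3, citing Table 18, says: "Per protocol, all adverse events occurring within 28 days of the third vaccination (Day 71) will be presented".

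**The looser sentence.** The protocol synopsis (Study Design) says that "a telephone follow-up will be performed at 6 months following receipt of the final vaccination to assess for adverse events", with no restriction to serious events.

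**The concern.** A percentage with an exact interval tells the reader that an outcome was looked for in the stated number of people over the stated period. In four of the six late-block rows that is only partly true. Serious events are sought, and they count as AEs. Mild and moderate events are not asked about, so they appear only if a subject volunteers them and the site records them.

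Safety is the trial's primary objective, and Table 18 is its in-text AE summary. Zeros or near-zeros there, each with an interval and a p-value, could be taken as evidence that milder late reactions were rare. The data would support a statement about serious events only. The p-values would compare groups on whatever happened to be volunteered.

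**Working it through.** **1. Period covered.** Day 223 − Day 71 = 152 days.

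**2. Rows set against collection rules.**

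| Late-block row | Serious events sought? | Non-serious events sought? |
|---|---|---|
| Any AE | Yes | No |
| Any AE, Grade 2+ | Yes | No |
| Any related AE | Yes | No |
| Any related AE, Grade 2+ | Yes | No |
| Any SAE | Yes | not applicable |
| Any related SAE | Yes | not applicable |

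Four rows in four treatment groups give 16 cells with partial ascertainment. If no non-serious event is volunteered, the any-AE row equals the any-SAE row and the related-AE row equals the related-SAE row.

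**3. The plan's own precision figure.** SAP section 5 gives 0–21% for no events in 16 subjects. The exact two-sided 95% upper limit for 0/n is 1 − 0.025^(1/n).

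- n = 16: 1 − 0.025^(1/16) = 20.6%, which rounds to the stated 21%.
- n = 12 (pooled placebo, 3 × 4): 1 − 0.025^(1/12) = 26.5%.

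The shell would print these limits beside a zero in an AE row. They are ordinary zero-event limits. They allow for sampling error and do not measure under-recording.

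**4. How far a printed rate could fall short.** The documents give no late AE rate and no spontaneous-report rate, so both are assumptions here. Expected printed rate = true rate × fraction of affected subjects recorded.

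| Assumed true 152-day AE rate | 0% recorded | 10% | 25% | 50% |
|---|---|---|---|---|
| 20% | 0% | 2% | 5% | 10% |
| 40% | 0% | 4% | 10% | 20% |
| 60% | 0% | 6% | 15% | 30% |

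**5. Whether the printed interval would exclude the truth.** Take n = 16 and an assumed true rate of 40%. The exact upper limit is 38.3% at 2/16 and 45.6% at 3/16, so the interval lies wholly below 40% when two or fewer subjects are recorded. With 25% recorded, the count is binomial with probability 0.40 × 0.25 = 0.10, and P(0, 1 or 2) = 0.185 + 0.329 + 0.275 = 0.79. The same calculation gives:

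| Fraction recorded (true rate 40%) | n = 16 | n = 12 |
|---|---|---|
| 0% | 1.00 | 1.00 |
| 10% | 0.98 | 0.92 |
| 25% | 0.79 | 0.66 |
| 50% | 0.35 | 0.28 |
| 100% | 0.02 | 0.02 |

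At a true rate of 20% the interval never excludes the truth, since even 0/16 has an upper limit of 20.6%. The point estimate is still too low.

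**6. Denominator.** If 3 of 16 subjects were not reached (assumption), zero events would have an upper limit of 1 − 0.025^(1/13) = 24.7% among those contacted, against 20.6% with all 16.

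**The case against.** **The AE rows are not empty.** A reader might infer that the 16 AE cells rest on no data at all. The documents do not support that: the footnote counts SAEs as AEs, and SAEs are sought at the call. Ascertainment is partial. This objection stands.

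**Unreached subjects.** A reader might also infer from the footnoted N that subjects not reached by telephone are counted as event-free. The SAP does not say so. SAP 6.3.1 lets safety denominators vary with the data available, SAP 6.5 rules out imputation, and Table 9 reports Day 223 completion by group. What remains is that the Table 18 footnote names the Safety Population and is silent on the late block, so the rule should be stated. It would not cure the main problem, because a subject who is reached is still not asked about non-serious events.

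**The call may bring in more than SAEs.** A serious new diagnosis or health problem need not meet the SAE definition, and SAP 6.2 plans a final analysis of everything through Day 223. This also stands. Keeping only the SAE rows could lose such reports, and the fix provides for them. The broader synopsis wording does not rescue the AE rows, because the sections that specify the questions confine them to serious matters.

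**Limited harm.** The block is labelled separately, and AE tests are planned only where applicable. SAP 4.2 says the trial is not designed to show group differences. With no events in any group, Fisher's test gives p = 1 and Pearson's is undefined, so an all-zero row creates no spurious difference. These points limit the consequence, but they do not make the AE rows interpretable as incidence.

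**Conclusion.** The point holds in this limited form. The late block of Table 18 reports AE incidence, with intervals and tests, for a period in which the plan seeks serious events only. It also conflicts with SAP 8.3, which gives the same table a Day 71 cut-off. The direction follows from the design: if any non-serious event occurs and goes unrecorded, the AE rows are too low. The amount cannot be derived from the documents, and the figures in steps 4 and 5 of the working only illustrate assumed rates.

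It would be tempting to conclude that the primary safety results are compromised. They are not. The unsolicited AE endpoint runs from Day 1 to Day 71, that block of Table 18 is unaffected, and the late SAE rows are valid for subjects who were contacted. This is a modest reporting defect that should be corrected before the tables are produced.

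**What to change.** In the late block of SAP Table 18:

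1. Keep the two SAE rows. If wanted, add one row for serious new diagnoses or hospitalizations reported at the call, so that those short of the SAE definition are not lost.
2. Remove the four AE rows with their rates, intervals and p-values. Put spontaneously reported non-serious events in Listing 10, which under SAP 8.3 already takes everything on the AE form.
3. Add a footnote that non-serious AEs were not solicited after Day 71 and that, consistent with SAP 6.3.1, the denominator for this block is subjects who completed the Day 223 contact, as counted in Table 9.

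In the protocol synopsis, align the sentence on the telephone follow-up with protocol 11.8.1.

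The cost is one edit to a table shell, one footnote and one sentence in the synopsis. No visit, question or data item changes.

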9.6.1. When and How to Withdraw Subjects

A subject may end his or her participation in the study at any time. If a subject withdraws, the investigator will make a reasonable effort to determine the reason for the withdrawal from the study and to complete termination procedures. Telephone calls, registered letters, and e-mail correspondence are considered reasonable effort. For subjects leaving the study, a targeted examination may be performed if medically indicated and if permitted by the subject.

A subject may be withdrawn for an AE or SAE resulting in a safety concern or for noncompliance with protocol requirements. When a subject withdraws or is withdrawn by the PI due to an AE that results in a safety concern, the sponsor must be notified within 72 hours. Investigators must follow specific policy at each institution regarding the timely reporting of AEs and SAEs to the local IRB (section 11.9.1.2). In all cases, the PI will make a reasonable effort to complete study termination procedures. Subjects who do not receive subsequent vaccine doses but who continue in follow-up for safety and immunogenicity are not considered to be withdrawn from the study.

If a subject meets withdrawal conditions for a concomitant medication violation or noncompliance, this should clearly be stated in the source document and the study termination eCRF.

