3.1. Study Objectives

3.1.1. Primary Objective

The primary objective of the study is to evaluate the safety of Invaplex_{AR}-DETOX administered by IM immunization. This will include an assessment of the tolerability and safety of Invaplex_{AR}-DETOX (or placebo) after each dose in terms of rates of solicited local and systemic adverse events (AEs) through 7 days post-vaccination (i.e., on the day of vaccination and 7 subsequent days), unsolicited AEs through 28 days post-final vaccination, hematology, serology, and chemistry abnormalities 7 days post-vaccination, and serious health problems or hospitalizations through approximately 6 months after final study vaccination.

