3.3. Study Definitions and Derived Variables

3.3.1. Adverse Event (AE)

An AE, as defined by the ICH guideline for GCP, is “Adverse event means any untoward medical occurrence associated with the use of a drug in humans, whether or not considered drug related.”

An AE is considered any adverse change or exacerbation from a baseline condition that occurs following the initial administration of an investigational product whether or not the event is considered to be related to the investigational product. Examples of this include but are not limited to the following:

- Adverse changes including new signs and symptoms, intercurrent illness modifying the clinical course, or the worsening of a baseline condition including the increased frequency of an event or an increased intensity of a condition
- Concomitant disease with onset or increased severity after the start of study product administration
- A new pattern in a preexisting condition occurring after the receipt of investigational product that may signal a clinically meaningful change
- Clinically significant changes in laboratory values

This definition includes exacerbations of pre-existing conditions. Stable pre-existing conditions which do not change in nature or severity during the study are not considered AEs; however, these should be reported as part of the medical history. However, if this condition deteriorates (e.g., increases in frequency or severity grade) during the study, it should be recorded as an AE.

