8.6. Clinical Laboratory Evaluations

The distribution of each laboratory value will be presented by time point and treatment group ([Table 31, Appendix A](#)), including mean, standard deviation, mean change, median, median change, and range. The severity and relationship to study product of each laboratory value will be summarized separately ([Table 32, Appendix A](#)). A listing of all values in subjects will be prepared ([Listing 11](#) and [Listing 12, Appendix C](#)).

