	Range				
Pre-Vaccination 1	N				
	Mean (SD)				
	Median				
	Range				
Day 7 Post-Vaccination 1	N				
	Mean (SD)				
	Median				
	Range				
	Mean change from baseline (SD)				
	Median change from baseline				
Day 7 Post-Vaccination 2	N				
	Mean (SD)				
	Median				
	Range				
	Mean change from baseline (SD)				
	Median change from baseline				
Day 7 Post-Vaccination 3	N				
	Mean (SD)				
	Median				
	Range				
	Mean change from baseline (SD)				
	Median change from baseline				
Final “on therapy” value	N				
	Mean (SD)				
	Median				
	Range				
	Mean change from baseline (SD)				
	Median change from baseline				

Baseline values are from pre-vaccination 1. If missing, then screening values will be used.

Table will also include:

Hematology

WBC Count ($10^6/\mu\text{L}$)*	RBC Count ($10^3/\mu\text{L}$)**	Hemoglobin (g/dL)*
Hematocrit (%)*	Platelet count ($10^3/\mu\text{L}$)	Absolute Neutrophils (cells/ μL)
Absolute Lymphocytes (cells/ μL)	Absolute Monocytes (cells/ μL)	Absolute Eosinophils (cells/ μL)
Absolute Basophils (cells/ μL)		

Chemistry

Sodium (mmol/L)	Potassium (mmol/L)*	Chloride (mmol/L)
BUN (mg/dL)	Creatinine (mg/dL)**	Bicarbonate (mmol/L)
Glucose (mg/dL)	AST (U/L)	ALT (U/L)

[Programming note: * reported to one decimal place, ** 2 decimal places. All others are integers].

Table 32: Final On Therapy Hematology and Serum Chemistry Severity Grading, by Treatment Group and Relationship¹ to IP - Safety Population

		InvaplexAR 2.5 μg (N=X)	InvaplexAR 10 μg (N=X)	InvaplexAR 25 μg (N=X)	Placebo (N=X)
		n (%)	n (%)	n (%)	n (%)
WBC					
All values	Normal				
	Abnormal ²				
	Mild				
	Moderate				
	Severe				
	Potentially Life-Threatening				
Not Related to IP	Mild				
	Moderate				
	Severe				
Related to IP	Mild				
	Moderate				
	Severe				
[other parameters]					

N=Number of subjects in the safety population.

¹ Relationship is assessed only for mild or greater values reported as adverse events.

² Outside the normal range but less than mild.

[See above for complete list of parameters]

A.3.3 Vital Signs

Table 33: Vital Signs: Descriptive Statistics by Visit and Treatment Group - Safety Population

	Pulse Rate (beats/min)				Systolic Blood Pressure (mm Hg)				Diastolic Blood Pressure (mm Hg)			
	Inva plexar-DETOX				Inva plexar-DETOX				Inva plexar-DETOX			
	2.5 µg (N=X)	10 µg (N=X)	25 µg (N=X)	Placebo (N=X)	2.5 µg (N=X)	10 µg (N=X)	25 µg (N=X)	Placebo (N=X)	2.5 µg (N=X)	10 µg (N=X)	25 µg (N=X)	Placebo (N=X)
Baseline¹												

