Listing 9: ALS IgG Antibody against *S. flexneri 2a* Invaplex

Study Group	Subject ID	Day -7		Baseline		Visit 03		Visit 06		Visit 09		Visit 11	
		Titer	Fold Rise	Titer	Fold Rise	Titer	Fold Rise	Titer	Fold Rise	Titer	Fold Rise	Titer	Fold Rise

C.3 Safety Listings

Listing 10: Adverse Events, by MedDRA System Organ Class (SOC) and Preferred Term (PT) [SOC1], [PT1]

Treatment Group	Subject ID	Adverse Event	Dose Number	Onset Day Post-Dose (Duration)	Severity	SAE	Relationship to Study Treatment	In Not Related, Alternative Etiology	Action Taken with Study Treatment	Subject Discontinued Due to AE?	Outcome
AE Summary/Comment:											

Listing 11: Clinical Lab Values – Hematology

Time Point ¹	Actual Study Day	Reference Range	Value	Change from Baseline	Severity	Clinically Significant	Comment
Subject ID: XXXXX, Treatment Group: YYYY							
[Parameter 1]							
Screening							
Day -7							
Day 8							
Day 29							
Day 50							
[Parameter 2]							
Screening							
Day -7							
Day 8							
Day 29							
Day 50							
[continue for other parameters]							

Listing 12: Clinical Lab Values – Chemistry

Similar format to Listing 11.

Listing 13: Vital Signs

Treatment Group	Subject ID	Time Point	Actual Study Day	Temperature (°C)	Systolic Blood Pressure (mm Hg)	Diastolic Blood Pressure (mmHg)	Heart Rate (beats/min)	Weight (kg)	Height (cm)

Listing 14: Concomitant Medications

Study Group	Subject ID	CM Number	Medication	Medication Start Day	Medication End Day	Ongoing at Study Start	Indication	Taken for an AE? (AE Description; Number)	Taken for a condition on Medical History? (MH Description; Number)	ATC Level 1 (ATC Level 2)

Listing 15: Pregnancy Report**Subject ID: XXXXX, Treatment Group: YYYYYY**

Maternal Information	
Pregnancy Number	
Date pregnancy reported	
Pregnancy test date	
Pregnancy status	
Estimated date of delivery	
Number of fetuses	
Actual date of delivery	
Maternal complications	
Action Taken with Study Product	
Study Status	
Comments	
Gravida and Para	
Gravida	
Pre-Term Birth	Extremely / Very early / Early / Late
Term Birth	Early / Full / Late / Post
Still Birth	
Abortion	Spontaneous / Miscarriage / Elective / Therapeutic
Major Congenital Anomaly with Previous Pregnancy?	
Live / Still Birth Outcomes (include only fields relevant to outcome)	
Fetus Number	
Pregnancy outcome	
Fetal Distress During Labor and Delivery?	
Delivery method	
Gestational Age at Live/Still Birth	
Size for Gestational Age	
Apgar Score, 1 minute	
Apgar Score, 5 minutes	

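### SAP Table 32 grades each laboratory test only at an undefined final on-therapy value, so a graded Day 8 or Day 29 value that resolves is not counted there

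*SAP*

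**What the plan says.** SAP 3.1.1 assesses safety after each dose, in rates that include "hematology, serology, and chemistry abnormalities 7 days post-vaccination". Protocol 8.6.1 schedules safety laboratory draws on Days 8, 29 and 50, that is, 7 days after each of the three doses.

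SAP 8.6 sets out two summaries. The first is Table 31: "The distribution of each laboratory value will be presented by time point and treatment group". The second is Table 32: "The severity and relationship to study product of each laboratory value will be summarized separately". The Table 32 shell (SAP Appendix A.3.2) carries the title "Final On Therapy Hematology and Serum Chemistry Severity Grading, by Treatment Group". Per test it shows normal, abnormal but below mild, and the severity grades, then blocks for values not related and related to product. It has no visit rows and no worst-grade row.

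Footnote 1 of that table reads "Relationship is assessed only for mild or greater values reported as adverse events". The AE definition in SAP 3.3.1 gives "Clinically significant changes in laboratory values" as one example of an AE. Listing 11 has a column headed "Clinically Significant", separate from the severity column.

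Protocol 12.1.1 uses the final on-therapy value for descriptive statistics (mean, median, changes, range), and Table 31 has a row for it. Neither document defines it.

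**The concern.** The Day 8 and Day 29 draws exist to detect changes after doses 1 and 2. A grading table limited to the final value cannot show them once they have resolved. No other planned final summary grades laboratory values by test regardless of AE status: Table 31 is ungraded, Tables 18-29 require an AE record, and Listings 11-12 are by subject.

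The undefined term adds ambiguity. For a completer with no unscheduled draw, the final value is presumably Day 50. Protocol 9.6.1 provides for "Subjects who do not receive subsequent vaccine doses but who continue in follow-up for safety and immunogenicity", and the SAP does not say whether the Day 50 value of such a subject is still on therapy. Protocol 11.5.4 allows extra specimens to confirm abnormal results, and the SAP does not say whether a repeat after Day 50 replaces the Day 50 value. Table 32 could therefore mix draws.

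At stake is whether a reader of the final tables can see, per test and after each dose, how many subjects had a graded value. As planned, that count has to be rebuilt from the listings.

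**Working it through.** **1. The plan's own precision figure.** SAP 5 gives 0-21% for no events in 16 subjects. The exact upper limit is 1 − 0.025^(1/16) = 20.6%, so it reproduces.

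**2. What Table 32 covers.** Each completer has three scheduled post-vaccination values per test, so a dose group of 16 has 3 × 16 = 48. Table 32 grades one per subject, or 16 of 48.

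**3. Where a resolved Day 8 or Day 29 grade appears.**

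| Output | Recorded as an AE | Not recorded as an AE |
|---|---|---|
| Tables 21-28 (maximum severity, by dose interval) | Yes | No |
| Table 29 (Grade 2 or greater, non-serious) | Listed if it qualifies | No |
| Table 31 | Ungraded, within the range for that draw | Same |
| Table 32 | As normal or below mild | Same |
| Listings 11-12 | Yes, by subject | Yes, by subject |

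The loss is thus the graded count per test and draw, and for values not recorded as AEs it is the whole graded count.

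**4. Can a graded value escape the AE tables?** Footnote 1 of Table 32 and the separate columns of Listing 11 imply that it can. Hemoglobin gives an example:
- A man enrolls at 12.9 g/dL. This is screening Grade 1 (12.5-13.1), which protocol 8.1 can allow.
- At Day 8 he has 12.6. By Table 5 that is 13.2 − 12.6 = 0.6 below the lower limit, Grade 1 (0.5-1.5).
- The fall from baseline is 12.9 − 12.6 = 0.3, under the 0.5 g/dL at which Table 5 footnote a records an AE.
- If Day 50 is again 12.9, he is 0.3 below the limit, under Grade 1, and no graded summary counts the Day 8 value.

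This route stays at Grade 1. Take the lowest Grade 1 baseline (12.5 for men, 11.0 for women) and the largest unrecorded fall to one decimal (0.4). The distance is 13.2 − 12.1 = 1.1 for men and 11.7 − 10.6 = 1.1 for women; Grade 2 starts at 1.6.

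**5. Size, under assumptions.** The documents give no rates. Suppose 2 of 16 subjects have a graded Day 8 value that resolves and no one is graded at the last draw. Table 32 shows 0/16 (exact 95% CI 0-20.6%); a worst-grade row would show 2/16 = 12.5% (1.6-38.3%).

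More generally, let q be the chance of a graded value per test and draw, and rho the correlation between the three draws (beta-binomial, completers only). With a = q(1−rho)/rho and b = (1−q)(1−rho)/rho, P(none of 3) is the product over i = 0, 1, 2 of (b+i)/(a+b+i). At rho = 0 it is (1−q)³, and at rho = 1 it is 1−q. The share with a graded value but none at the last draw is 1 − P(none) − q.

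| q | rho 0 | rho 0.5 | rho 1 |
|---|---|---|---|
| 2% | 3.9% | 1.6% | 0 |
| 5% | 14.3 − 5.0 = 9.3% | 8.9 − 5.0 = 3.9% | 0 |
| 10% | 17.1% | 7.35% | 0 |

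At q = 5%, that is 1.5, 0.6 and 0 subjects per group of 16. If a share r of these subjects is recorded as having an AE, multiply by (1 − r). At r = 90% the 9.3% becomes 0.9% (0.15 subjects) and the 3.9% becomes 0.4% (0.06 subjects).

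**The case against.** The strongest reply is that the laboratory endpoint in SAP 3.2.1.1 is worded as laboratory-based AEs, and these are fully reported by maximum severity and dose interval, with exact intervals. The headings of Tables 5 and 6 present the grades as AE coding, so most graded values may be recorded as AEs. Table 31 gives the range at each draw. For tests without sex-specific limits, comparing the extremes with Tables 5 and 6 shows whether any graded value occurred, though not how many. The safety review team also sees laboratory abnormalities within 7 days of each dose (SAP 6.6), and related abnormalities that meet the criteria in protocol 8.10 trigger a review. All of this stands. It narrows the gap but does not supply a graded count per test and draw in the final tables.

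A reader might infer three stronger things that the documents do not support.

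- **That Table 32 contradicts SAP 8.6.** In the sentence on Table 31, each laboratory value means each test. Read the same way, the sentence on Table 32 promises severity per test, and the shell gives that. The layout may also follow protocol 12.1.1, which mentions final on-therapy values and, separately, a split by relationship. It is a weak choice of time point, not a certain contradiction.
- **That two thirds of post-vaccination values are graded in no summary.** Step 2 concerns Table 32 alone; graded values recorded as AEs appear in Tables 21-28.
- **That the hemoglobin case is certain.** Protocol 11.5.4 makes the scale a guideline and leaves final grading to the principal investigator. Leaving a 0.3 g/dL fall out of the AE count is also what footnote a intends. The case shows a possible route, at Grade 1 only.

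**Conclusion.** The point holds as a reporting gap. Table 32 grades laboratory values by test at one undefined time point, while the primary objective looks 7 days after each dose. Grades at Day 8 or Day 29 that resolve by the last draw drop out of the only summary that grades values regardless of AE status.

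The size is unknown. It is zero if abnormalities always persist to the last draw, and close to zero if nearly all graded values are recorded as AEs. The range of 0 to 17.1% of subjects per test rests wholly on assumed values of q, rho and r, and is evidence of possible size only. No hypothesis test, analysis population or escalation decision changes. That supports a cheap improvement to the final tables, not a claim that laboratory safety goes unreported.

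**What to change.** Retitle and reshape Table 32. Per test and treatment group, show:

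1. the baseline grade;
2. the grade at each of Days 8, 29 and 50;
3. the worst post-baseline grade, including unscheduled draws.

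Present items 2 and 3 as a shift from baseline, or as the count with a grade higher than baseline. Protocol 8.1 can admit subjects with Grade 1 abnormalities, and a plain worst grade would count stable pre-existing values as post-vaccination findings. Use subjects with a value at that draw as the denominator. Add exact 95% CIs, which SAP 8 specifies for categorical safety measures and the shell lacks. Add the Grade 4 row missing from the related and not-related blocks.

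Keep the final on-therapy statistics in Table 31, where protocol 12.1.1 calls for them, and define the term there. The definition should cover subjects who miss dose 2 or 3 but stay in follow-up, and repeat draws after Day 50. One sentence in SAP 8.6 should say whether each laboratory value means each test or each result.

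The cost is one title, one shell and its program, one definition and one sentence. The grades are already in Listings 11-12. The downside is a longer table.
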